#### 4.3. Determination of Sample Size

For this Phase I Expansion study, up to approximately 185 patients will be enrolled among the different tumor types as outlined below:

# 5. STUDY PERIODS, TREATMENT REGIMENS, AND POPULATIONS FOR ANALYSIS

#### 5.1. Study Periods

The study periods are defined in the table 4 below.

**Table 4.** Definition of Study Periods for Analysis

Period	Definition
Baseline / Screening	From the day of ICF signature (up to 28 days before first dose) to the day and time of the first dose of study drug.
On-treatment	From the date of first dose of study therapy through 30 days after the last dose of study therapy. Unless otherwise specified, the on-treatment period will be the basis for the summaries of safety.

Abbreviations: ICF=informed consent form.

### **5.2.** Treatment Groups

There are 8 disease groups in this Phase I Expansion study as described in section 4.1 of this SAP. 20 mg QD of TAS-120 has been selected as the dose for each of the 8 disease groups.

In addition, in early portion of the Phase I Expansion study, a small number of patients were treated with 16 mg DQ and then followed by 20 mg QD.

### **5.3.** Populations for Analysis

- **Safety Population:** will include all patients who received at least 1 dose of TAS-120. This population will be the primary population for safety evaluation.
- Pharmacokinetics and Pharmacodynamics Population: will consist of all patients who received TAS-120 and have TAS-120 evaluable plasma and/or urine data. All such patients will be evaluated for PK and pharmacodynamics unless significant protocol deviations have impacted the data or key dosing information is missing.
- Efficacy Population: all treated Patients (Safety Population).

## **5.4.** Timing of Analysis

The final analysis will be performed when at least 90% of all treated patients had 4 months of follow-up.

The timing of the interim analysis please referred to Section 4.3 Determination of Sample Size of this SAP.

#### 6. STATISTICAL ANALYSIS

#### **6.1.** General Methods

All relevant data will be presented in patient level data listings.

All categorical (binary and ordinal) data will be summarized by tumor type groups using frequency counts and percentages of patients. Percentage will be calculated based on groups in the study population as the denominator. The continuous variables will be summarized using number of non-missing observation (n), mean, standard deviation (SD), median, minimum and maximum unless otherwise specified. The number of events and censorings will be reported for time-to-event analysis. All estimations will include a point estimate and the corresponding 95% confidence interval.

Summary tables will be presented by the disease type. Data listings will be presented with the groups and patient ID. The tables by sub-groups such as: age groups, gender, races, ECOG categories, and will be also summarized.

Analysis Cohort based on disease type (disease group 1 through group 8) are assigned as follows. Unless otherwise specified, by-cohort analysis will be included in tables and figures.

- Cohort 1: Patients with Cholangiocarcinoma (CCA). It combines disease group 1 to 4
- Cohort 2: Patients with primary CNS tumor. It's the patients from disease group 5
- Cohort 3: Patients with advanced urothelial carcinoma. It's the patients from disease group 6
- Cohort 4: Patients with breast cancer or gastric cancer. It's the patients from disease group 7
- Cohort 5: Patients with the tumor types in disease group 8, harboring FGFR gene fusions or activating mutations
- Cohort 6: Patients not included in cohort 1 to cohort 5

For concomitant medications and adverse events, the cycles are determined based on their start/onset dates. For other collected data, the cycles are determined based on their visit dates. When there are multiple laboratory records for a scheduled visit, the one closest to the target date (relative to the Day 1 in that cycle) will be used for analysis. If there are two or more records with the same time period to the target date, the later one will be used for analysis.

Time to event distribution (e.g. progression free survival, overall survival, time to response, and duration of response) will be estimated using Kaplan Meier techniques. When appropriate, the median along with the corresponding log-log transformed 95% CI will be estimated. Rates at fixed time points will be derived from the Kaplan Meier estimate and corresponding confidence interval will be derived based on Greenwood formula for variance derivation and on log-log transformation applied on the survivor function S(t). Confidence intervals for binomial proportions, ORR and DCR, will be derived using the Clopper-Pearson method.

For patients who were also treated with 16 mg QD during early portion of the Phase I Expansion of the study, separate analysis will be presented.

All the analyses of efficacy, safety, and PK data for this study will be performed using SAS® statistical software package, Version 9.3 or a later version.

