Please note: for patients who discontinued treatment for reasons other than disease progression, tumor assessments should be continued until radiologic disease progression or initiation of new anticancer therapy (whichever occurs first).

Solid Tumors

Measurements of solid tumors will be performed throughout study treatment using Response Evaluation Criteria in Solid Tumors (RECIST) guidelines (version 1.1, 2009). Radiographic tumor assessments (computed tomography [CT] scan with contrast will be performed at baseline and at the end of every 2 cycles (up to + 2 weeks) up to Cycle 4 (or as clinically indicated). Following Cycle 4, CT scans will be performed after every 3 cycles (\pm 7 days) or as clinically indicated, and at study completion.

Brain Tumors

Patients with brain tumors will be assessed using Response Assessment in Neuro-Oncology (RANO) criteria (2010). Patients with brain tumors will be evaluated for response by contrast magnetic resonance imaging (MRI) (gadolinium-based magnetic resonance imaging [Gd-MRI]). All MRIs should be performed when the patient is on a stable dose of steroids. Gd-MRI will be performed at baseline and at the end of every 2 cycles (up to + 2 weeks) up to Cycle 4 (or as clinically indicated). Following Cycle 4, Gd-MRI scans will be performed after every 3 cycles (\pm 7 days) or as clinically indicated, and at study completion.

Neurological examination for patients with brain tumors must always be performed within one week of the date of the Gd-MRI as part of the response assessment.

Endpoints

Phase 1 Expansion: the primary endpoint is ORR in each treatment group (and EPR for primary CNS tumors) and the secondary endpoints of DOR, DCR, PFS, and OS in each treatment group.

Phase 2: the primary endpoint is ORR and the secondary endpoints of DOR, DCR, PFS, PROs and OS.

Primary endpoints will be based on the independent review of images by the Core Imaging Laboratory. In addition, for the Phase 2 part of the study, sensitivity analyses for some key efficacy endpoints (e.g., ORR, and PFS) will be performed based on investigators or local radiologist assessments.

Statistical Methods:

Analysis Populations

The *Safety Population* will include all patients who received at least 1 dose of TAS-120. This population will be the primary population for safety evaluation.

The *DLT Evaluable Population* was defined for Phase 1 Dose Escalation only; Phase 1 Dose Escalation has been completed as of Amendment 6.

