The *PK and Pharmacodynamic Population* will consist of all patients who received TAS-120 and have TAS-120 evaluable plasma and/or urine data. All such patients will be evaluated for PK and pharmacodynamics unless significant protocol deviations have impacted the data or key dosing information is missing. Changes to the procedures, which may impact the quality of PK and pharmacodynamic data, will be considered “PK and pharmacodynamics relevant protocol deviations.” Examples include sample processing errors that lead to inaccurate bioanalytical results and/or inaccurate dosing on the day of PK and pharmacodynamic sampling.

The *Efficacy Population* is defined for each portion of the study as follows:

- Phase 1 Dose Escalation: All treated patients (safety population)
- Phase 1 Expansion: All treated patients (safety population)
- Phase 2: All treated iCCA patients with confirmed FGFR2 gene fusions or other FGFR2 rearrangements

Efficacy Analyses

For Phase 1 Expansion, efficacy data for the primary endpoint of ORR (and EPR for primary CNS tumors), and secondary endpoints of PFS, DCR, DOR, and OS will be summarized for each treatment group.

For Phase 2, efficacy data for the primary endpoint of ORR and secondary endpoints of DOR, PFS, DCR, Patient-Reported Outcomes (PROs) and OS will be summarized. For PROs, the analysis of a EuroQol-5D measure of health-related quality of life (EQ-5D) and the European Organization for Research and Treatment of Cancer Quality of Life Questionnaire (EORTC QLQ-C30) will be performed in all treated patients who have an assessment at baseline and at least one subsequent assessment.

Determination of Sample Size:

Phase 1 Dose Escalation:

There were 86 patients enrolled in the Phase 1 Dose Escalation part of the study which has been completed as of Amendment 6.

Phase 1 Expansion:

Up to approximately 185 patients will be enrolled as outlined below:

CCI

Phase 2:

Approximately 100 iCCA patients with FGFR2 gene fusions or other FGFR2 rearrangements will be treated.

CCI

Interim Analyses:

Interim reviews of safety will be performed approximately every 3 months throughout the study, until the interim analysis cut-off. These interim reviews will be performed by a Safety Review Committee (SRC), comprising, at minimum:

- 1 independent investigator and 1 independent statistician, neither of whom is directly involved in the conduct or analysis of the study; and

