6.2. Phase 1 Expansion

Primary

- To evaluate ORR in cholangiocarcinoma (intra-hepatic [iCCA] or extra-hepatic [eCCA]) patients with tumors harboring FGFR2 gene fusions or other FGFR abnormalities.
- To evaluate ORR and EPR (defined as progression-free rate at the end of Cycle 2) in patients with primary CNS tumors harboring FGFR gene fusions or FGFR1 activating mutations ([Appendix A](#)).
- To evaluate ORR in a basket of tumor types with tumors harboring FGFR2 amplifications.
- To evaluate ORR in a basket of tumor types with tumors harboring any FGFR gene fusions or activating mutations [Appendix A](#)).

Secondary

- To investigate the safety of TAS-120.
- To evaluate DCR, DOR, PFS, and OS in each treatment group.

CCI

6.3. Phase 2

Primary

- To confirm ORR in iCCA patients with FGFR2 gene fusions or other FGFR2 rearrangements based on independent central radiology review.

Key secondary

- To evaluate DOR

Other secondary

- To evaluate the safety and tolerability of TAS-120.
- To evaluate DCR, PFS, and OS
- To evaluate Patient-Reported Outcomes (PROs)

CCI

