7.1.1. Phase 1 Expansion

TAS-120 will be administered orally at 20 mg, QD in 21-day cycles. Approximately 185 patients will be enrolled. Patients are assigned to one of 8 groups based on tumor type and FGFR aberration, as described below.

Additional patients may be enrolled to any of the groups as promising clinical activity emerges.

- Group 1 (Enrollment suspended as of Amendment 7): Patients with intrahepatic or extrahepatic CCA harboring FGFR2 gene fusions
- Group 2: Patients with intrahepatic or extrahepatic CCA harboring FGFR2 gene fusions that have not received or received less than 1 cycle of prior chemotherapy (due to intolerance or patient refusal)
- Group 3 (Enrollment suspended as of Amendment 7): Patients with intrahepatic or extrahepatic CCA harboring FGFR2 gene fusions that have been treated with prior FGFR inhibitors
- Group 4 (Enrollment suspended as of Amendment 7): Patients with intrahepatic or extrahepatic CCA harboring FGFR abnormalities other than FGFR2 gene fusions (for example, mutations, rearrangements, or amplifications)
- Group 5: Patients with primary CNS tumors harboring FGFR gene fusions or FGFR1 activating mutations
- Group 6 (Enrollment suspended as of Amendment 7): Patients with advanced urothelial carcinoma harboring FGFR3 gene fusions or FGFR3 activating mutations
- Group 7: Patients with any tumor type not included in one of the prior groups, harboring FGFR2 amplification (no minimum number of copies) (Figure 2).
- Group 8 (Enrollment suspended as of Amendment 7): Patients with any tumor type not included in one of the prior groups, harboring FGFR gene fusions or activating mutations

Figure 2: Group 7 Tumor Types

[figure not shown]

7.1.2. Phase 2

During Phase 2, TAS-120 will be administered orally at 20 mg, once daily (QD) in 21-day cycles.

The overall study design for Phase 2 of the study is described in [Figure 3](#).

Figure 3: Study Schema for Phase 2

ORR = Objective response rate; PFS = Progression-free survival; DCR = Disease control rate; DOR = Duration of response; OS = Overall survival; PROs = Patient-Reported Outcomes; PK = Pharmacokinetics.

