#### 4. STUDY DESCRIPTION

#### 4.1. Summary of Study Design

This is an open-label, nonrandomized, and Phase I Expansion study of TAS-120, evaluating the efficacy, safety, and antitumor activity of the RP2D of TAS-120 in patients with advanced solid tumors with FGF/FGFR-related abnormalities who have failed all standard therapies or for whom standard therapy does not exist or is not tolerated.

As of Amendment 6, the Phase 1 Dose Escalation Phase is completed and MTD/RP2D of 20 mg QD was established.

TAS-120 will be administered orally at 20 mg, QD in 21-day cycles. Approximately 185 patients will be enrolled. Patients will be assigned to one of 8 disease groups based on diagnosis, prior therapy, and FGFR aberration:

- Group 1 (Enrollment suspended as of Amendment 7): Patients with intrahepatic or extrahepatic CCA harboring FGFR2 gene fusions or rearrangements.
- Group 2: Patients with intrahepatic or extrahepatic CCA harboring FGFR2 gene fusions or rearrangements that have not received or received less than 1 cycle of prior chemotherapy (due to intolerance or patient refusal)
- Group 3 (Enrollment suspended as of Amendment 7): CCA (iCCA or eCCA) with FGFR2 gene fusions or rearrangements treated with prior FGFR inhibitors
- Group 4 (Enrollment suspended as of Amendment 7): CCA (iCCA or eCCA) with other FGFR abnormalities, i.e., gene mutations, rearrangements or amplifications
- Group 5: Patients with primary CNS tumors harboring FGFR gene fusions or FGFR1 activating mutations
- Group 6 (Enrollment suspended as of Amendment 7): Patients with advanced urothelial carcinoma harboring FGFR3 gene fusions or FGFR3 activating mutations
- Group 7: Patients with any tumor type not included in one of the prior groups, harboring FGFR2 amplification (no minimum number of copies).
- Group 8 (Enrollment suspended as of Amendment 7): Patients with any tumor type not included in one of the prior groups, harboring FGFR gene fusions or activating mutations

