### **6.4.** Efficacy Analyses

#### 6.4.1. Primary Efficacy Analyses

The primary endpoint, Objective Response Rate (ORR), defined as the proportion of patients who achieved best overall response of partial response (PR) or complete response (CR) in the Efficacy Population for solid tumor patients. It will be calculated from the best of overall response recorded from the start of treatment until progression disease or start of subsequent new anticancer treatment. The overall response can be derived based on target lesion response, non-target response as well as the emergence of new lesion for patients with measurable disease at baseline. Rules for Overall Response derivation is summarized in Table 5.

A minimum of 4-week interval between two tumor measurements is required to confirm PR or CR. A minimum of 6-week interval between initial of treatment (first dose date) and tumor measurement is required for SD. The confirmation rule is shown in Table 5.

PD

PD

Statistical Analysis Plan (Phase I Expansion)—Protocol: TPU-TAS-120-101

The 95% confidence interval (binomial proportion confidence interval) for ORR will be constructed with Clopper-Pearson 95% CI.

The ORR summary based on Independent Review will be presented for iCCA patients by the 4 categories of: with FGFR2 rearrangement, without FGFR2 rearrangement, with FGFR2 rearrangement with GEM/CIS and without FGFRi Prior Treatment, with FGFR2 rearrangement with FGFRi prior treatment.

In addition, ORR will be presented based on data from the Investigator Review.

Later Response Confirmed Response Earlier Response (to be confirmed) (confirmation) CR CR CR CR Not CR or missing SD PR CR or PR PR PR SD or PD or missing SD SD and then PR (only one SD in between) PR PR SD n/a – no confirmation needed SD n/a – no confirmation needed

Table 5. Confirmation Rule for Overall Response of PR and CR

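### The Expansion SAP tabulates cholangiocarcinoma Groups 1–4 as one pooled cohort plus iCCA-only categories, so the group-level ORR named in the protocol synopsis is not planned, most clearly for Group 2

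*SAP*

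**What the plan says.** **Protocol.** The Synopsis (Endpoints) reads "Phase 1 Expansion: the primary endpoint is ORR in each treatment group (and EPR for primary CNS tumors"). Under Efficacy Analyses it adds that "secondary endpoints of PFS, DCR, DOR, and OS will be summarized for each treatment group". Section 7.1.1 fixes the groups: "Patients are assigned to one of 8 groups based on tumor type and FGFR aberration, as described below". Four of the eight are cholangiocarcinoma groups and admit both iCCA and eCCA: Group 1 (FGFR2 fusion), Group 2 (fusion, with no chemotherapy or under one cycle), Group 3 (fusion, previously given an FGFR inhibitor) and Group 4 (FGFR abnormalities other than FGFR2 fusions, with rearrangements given as an example). Section 6.2 words the primary cholangiocarcinoma objective more broadly, as ORR in "patients with tumors harboring FGFR2 gene fusions or other FGFR abnormalities", but sets the secondary objectives per treatment group.

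**Expansion SAP.** Section 6.1 defines "Cohort 1: Patients with Cholangiocarcinoma (CCA). It combines disease group 1 to 4" and states: "Unless otherwise specified, by-cohort analysis will be included in tables and figures". Section 6.4.1 adds: "The ORR summary based on Independent Review will be presented for iCCA patients by the 4 categories of" FGFR2 rearrangement present; absent; present with prior GEM/CIS and no FGFR inhibitor; present with a prior FGFR inhibitor. Section 6.4.2 uses the same four for the secondary endpoints. Section 4.1 adds rearrangements to the definitions of Groups 1–3, while Group 4 remains "CCA (iCCA or eCCA) with other FGFR abnormalities, i.e., gene mutations, rearrangements or amplifications". Section 7, on changes to the planned analysis, lists the wording of Groups 1–3 and the timing of the final analysis; it does not mention pooling.

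**The concern.** The synopsis names the group as the unit of analysis for the primary endpoint, and the SAP's tables use a coarser unit for half of the groups. Groups 1–4 differ in prior chemotherapy, prior FGFR inhibition and type of aberration, and each of these could plausibly change the response rate. A pooled rate over them depends on how many patients of each kind were enrolled.

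What is at stake is mainly Group 2. It is the one cholangiocarcinoma group still open after Amendment 7 (Protocol 5.5 and 7.1.1), and it asks about a population that the other three groups do not represent. A second loss is eCCA, which all four groups admit and which no planned table shows separately.

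**Working it through.** There is no stated figure to reproduce: the group sizes and design rates are not visible in the public text, and the point does not depend on them. The check is a comparison of groups with planned tables, followed by an illustration.

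**Step 1. Match each group to the nearest planned ORR summary.** I read the SAP's rearrangement categories as including fusions.

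| Protocol group | Nearest SAP summary besides the pool | What it misses |
|---|---|---|
| 1 | iCCA, rearrangement, GEM/CIS, no FGFR inhibitor | eCCA; patients whose prior chemotherapy was not GEM/CIS |
| 2 | None; its iCCA patients sit inside the broad rearrangement-present category | A separate estimate, for iCCA and eCCA alike |
| 3 | iCCA, rearrangement, prior FGFR inhibitor | eCCA |
| 4 | iCCA without rearrangement | eCCA; patients with rearrangements, whom the protocol places here |
| 5, 6, 7, 8 | Cohorts 2, 3, 4, 5 | No pooling (Cohort 4's label is narrower than Group 7's definition) |

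Group 2 cannot be recovered exactly by subtraction. Taking the two prior-therapy categories away from the rearrangement-present category leaves iCCA patients with neither GEM/CIS nor an FGFR inhibitor. That remainder would include patients treated with other chemotherapy, could miss Group 2 patients who had part of one GEM/CIS cycle, and contains no eCCA.

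**Step 2. Look for group-level output elsewhere.** SAP 6.1 carries the group into data listings, and 6.4.3 lists best response and duration by patient. These allow a reader to count, but give no estimate or interval.

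**Step 3. Illustrate the effect of pooling.** All rates and sizes here are assumptions. Take equal groups of size n, with pooled ORR = total responders / 4n and exact (Clopper-Pearson) 95% intervals.

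Rates of 30%, 50%, 10%, 10% in Groups 1–4:
- n = 10: (3+5+1+1)/40 = 25% (12.7–41.2%); Group 2 alone 5/10 = 50% (18.7–81.3%).
- n = 20: 20/80 = 25% (16.0–35.9%); Group 2 alone 10/20 = 50% (27.2–72.8%).
- n = 30: 30/120 = 25% (17.5–33.7%); Group 2 alone 15/30 = 50% (31.3–68.7%).

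A common rate of 30%, n = 10: pooled 12/40 = 30% (16.6–46.5%); Group 2 alone 3/10 = 30% (6.7–65.2%). Pooling then leaves the estimate unchanged and narrows the interval.

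The visible response count for FGFR2-fusion disease, 3/14 = 21.4% (exact 95% CI 4.7–50.8%; Protocol 5.6), comes from iCCA fusion patients across the Phase 1 portions. It is not a rate for any one group and says nothing about differences between groups.

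**The case against.** The strongest reply is that the SAP follows the protocol's objective. Protocol 6.2 asks for ORR in cholangiocarcinoma as a whole, and Cohort 1 answers that. The per-group wording for the primary endpoint stands in the synopsis; sections 10.1 and 12.2.2 give ORR with no group qualifier. This part stands: the protocol is not uniform. A reader might infer that the SAP fails to deliver the primary endpoint altogether, and the documents do not support that. The synopsis commitment nevertheless remains, the secondary objectives in 6.2 are per group, and the SAP neither meets these nor records a departure.

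Second, the iCCA categories undo much of the mixing. That is fair for Groups 1 and 3 within iCCA, and partly for Group 4. It does not hold for Group 2 or for eCCA.

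Third, SAP 6.1 also speaks of summarizing categorical data by tumor type groups, and the sample-size text in SAP 4.3 is not visible. The first phrase is ambiguous, but the explicit cohort rule follows it in the same section. Whether the unseen text specified analyses of Groups 1–4 cannot be known, so the conclusion is limited to the visible plan.

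Fourth, on definitions, the word other in the SAP's Group 4 can be read as excluding FGFR2 rearrangements already placed in Groups 1–3, so overlap is not certain. Even on that reading, patients whom the protocol puts in Group 4 move to Groups 1–3. Reverting to the protocol text would not by itself give exclusive groups: Group 1 as worded also covers patients who meet Group 2 or Group 3.

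**Conclusion.** The gap is real and limited. For four of eight groups, the visible Expansion SAP plans no ORR table by the group defined in the protocol. Groups 1 and 3 and part of Group 4 have iCCA approximations; Group 2 is not isolated; eCCA appears only in the pool. Groups 5–8 are unaffected.

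The cost of pooling cannot be stated as a fact. In the illustration it runs from no distortion (equal rates) to a pooled 25% against 50% in Group 2, and the second value only restates the assumed rates. A reader might infer that the pooled ORR is known to understate Group 2; no figure in the documents shows that. The case rests on the synopsis wording, on the SAP's default of cohort tables, and on the absence of any recorded change. It should be corrected before analysis, and it does not invalidate the pooled result as an answer to the cholangiocarcinoma-wide objective.

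**What to change.** In the Expansion SAP, add ORR with Clopper-Pearson 95% CI, plus DOR, DCR and PFS, for each of Groups 1–4 by assigned group, with iCCA and eCCA patients both included. Keep Cohort 1 and the four iCCA categories alongside.

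Reconcile the group definitions in SAP 4.1 with Protocol 7.1.1 and 7.2.1, in particular where rearrangements belong, and state the assignment rule so that each patient counts in one group only. Align the protocol's synopsis and body on whether the primary endpoint is per group. If pooling is what is intended, record it with a reason in SAP section 7.

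The cost is a few more tables from data already collected. Intervals in small groups will be wide (18.7–81.3% for 5 of 10 in the illustration) and should be shown as such.

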7.2.1. Inclusion Criteria

A patient must meet all of the following inclusion criteria to be eligible for enrollment in this study:

1. Provide written informed consent.
2. Is ≥ 18 years (or according the country's regulatory definition for legal adult age).
3. Has histologically or cytologically confirmed, locally advanced, metastatic cancer meeting the following criteria:
 - a. Phase 1 Expansion
 - i. Patient has failed (or in the case of Group 2, failed or refused) all standard therapies or standard therapy does not exist or is not tolerated.
 - ii. Patient is eligible for 1 of the following enrollment groups, based on diagnosis, prior therapy, and FGF/FGFR aberrations as shown:
 - a. **Group 1 (Enrollment Suspended as of Amendment 7):** Patient has intrahepatic or extrahepatic cholangiocarcinoma harboring FGFR2 gene fusions.
 - b. **Group 2:** Patient has intrahepatic or extrahepatic cholangiocarcinoma harboring FGFR2 gene fusions, and has not received or received less than 1 cycle of prior chemotherapy (due to intolerance or patient refusal).
 - c. **Group 3 (Enrollment Suspended as of Amendment 7):** Patient has intrahepatic or extrahepatic cholangiocarcinoma harboring FGFR2 gene fusions and has received prior treatment with FGFR inhibitors.

- d. **Group 4 (Enrollment suspended as of Amendment 7):** Patient has intrahepatic or extrahepatic cholangiocarcinoma harboring FGFR abnormalities **other than** FGFR2 gene fusions (for example, mutations, rearrangements, or amplifications).
 - e. **Group 5:** Patient has a primary CNS tumor harboring FGFR gene fusion or FGFR1 activating mutation and fulfills the following criteria (i and ii):
 - i. Patients who are presenting in recurrence or relapse must have at least one measurable enhancing mass lesion with 2 perpendicular diameters of at least 10 mm documented on baseline contrast magnetic resonance imaging (MRI) (gadolinium-based MRI).
 - ii. Patients should be on a stable dose of steroids for at least 7 days prior to obtaining the baseline contrast MRI of the brain and at least 7 days prior to starting study drug.
 - f. **Group 6 (Enrollment Suspended as of Amendment 7):** Patient has advanced urothelial carcinoma harboring FGFR3 fusions or FGFR3 activating mutations.
 - g. **Group 7:** Patient has any tumor type not included in one of the prior groups, harboring FGFR2 amplification (no minimum number of copies).

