The Phase I Expansion part of the study included a total of 8 disease groups enrolling different patient populations; 3 of these groups remain open as of Amendment 7 to this protocol. This includes a group of patients with cholangiocarcinoma (CCA), a group of patients with primary CNS tumors harboring FGFR gene fusion or FGFR1 activating mutation, and 1 basket cohort including patients with solid tumors that harboring FGFR2 amplifications.

Expansion in patients with CCA is based upon clinical evidence of preliminary anti-tumor activity in this condition observed during the Phase I Dose Escalation portion of the study.

The group of patients with primary CNS tumors is included on the basis of nonclinical studies demonstrating the viability of FGFR1 activating mutations and FGFR gene fusions as therapeutic targets in human gliomas.

Group 7 (basket of tumor types harboring FGFR2 amplifications) was designed based on research suggesting that response to treatment targeting the FGFR may be increased across a wide range of different solid tumors harboring this form of mutation. As FGFR2 amplifications are most common in ovarian and upper gastrointestinal tumors, these 2 cancer types will be included in distinct subgroups of Group 7, with a third subgroup encompassing all other tumors with FGFR2 amplifications.

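### The Expansion SAP defines Cohort 4 both as breast or gastric cancer and as disease group 7, which are different sets of patients

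*SAP*

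**What the plan says.** The Phase 1 Expansion SAP, section 6.1 (General Methods), maps the eight disease groups to six analysis cohorts. The fourth reads: "Cohort 4: Patients with breast cancer or gastric cancer. It's the patients from disease group 7". The last is a remainder: "Cohort 6: Patients not included in cohort 1 to cohort 5". The same section makes by-cohort presentation the default for tables and figures.

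Elsewhere Group 7 is described differently:

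- Expansion SAP, section 4.1: "Group 7: Patients with any tumor type not included in one of the prior groups, harboring FGFR2 amplification (no minimum number of copies").
- Protocol, section 7.1.1: "Group 7: Patients with any tumor type not included in one of the prior groups, harboring FGFR2 amplification". Inclusion criterion 3 in section 7.2.1 applies the same test.
- Expansion SAP, section 2, which matches the rationale in protocol section 5.5, puts "ovarian and upper gastrointestinal tumors, these 2 cancer types will be included in distinct subgroups of Group 7" and gathers the remaining FGFR2-amplified tumour types into one more.

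Section 3.1.1 of the Expansion SAP lists the objective response rate (ORR) in the FGFR2-amplified basket as a primary objective.

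**The concern.** The Cohort 4 entry gives a tumour-type rule and a group-number rule as if they were the same, and they select different patients. Ovarian cancer is one of the two tumour types that the plan singles out in Group 7, yet it lies outside the breast/gastric wording.

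This matters because the cohort definition sets a denominator. In the visible text of section 6.4.1, the only ORR tables specified by patient category are for intrahepatic cholangiocarcinoma. Group 7 reaches the ORR output through the by-cohort default in section 6.1, so the Cohort 4 definition decides who counts towards the FGFR2-amplification primary objective. Group 7 was also one of the three expansion groups still open as of Amendment 7 (protocol section 5.5).

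The study is open-label. A denominator that can be read two ways leaves a choice to be made once responses are known.

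**Working it through.** The plan states no figure to reproduce, and no formula applies. The check sets the definitions side by side and follows each type of patient through both rules.

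**Inputs.** The Cohort 4 and Cohort 6 entries (Expansion SAP 6.1); the Group 7 and Group 8 definitions (Expansion SAP 4.1, protocol 7.1.1 and 7.2.1); the three Group 7 subgroups (Expansion SAP 2, protocol 5.5).

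**Step 1: allocate patients under each rule.**

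| Patient | By tumour-type wording | By group number |
|---|---|---|
| Group 7, ovarian | Cohort 6 | Cohort 4 |
| Group 7, upper GI, gastric | Cohort 4 | Cohort 4 |
| Group 7, upper GI, not gastric | Cohort 6 | Cohort 4 |
| Group 7, other, breast | Cohort 4 | Cohort 4 |
| Group 7, other, not breast | Cohort 6 | Cohort 4 |
| Group 8, breast or gastric with an FGFR fusion or activating mutation | Cohorts 4 and 5 | Cohort 5 |

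The rules agree for Group 7 patients with gastric or breast cancer and disagree in the other four rows. Of the three planned subgroups, the tumour-type wording loses all of the ovarian one and part of each of the other two.

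**Step 2: see what is left for Cohort 6.** Under the group rule, Cohort 1 takes Groups 1–4 and Cohorts 2, 3, 4 and 5 take Groups 5, 6, 7 and 8. That uses all eight groups, and each expansion patient is assigned to one of them. Cohort 6 would then be empty apart from any unassigned patients. Under the tumour-type rule it would receive the Group 7 patients shown above.

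**Step 3: look for a later decision to narrow Group 7.** The list of changes in Expansion SAP section 7 touches Groups 1, 2 and 3 and the timing of the final analysis. It does not mention Group 7. No other visible definition limits Group 7 to breast or gastric cancer.

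**Step 4: look for the three subgroups in the analysis sections.** Section 6.1 names age, gender, race and ECOG subgroups. Neither 6.1 nor 6.4 names ovarian, upper GI and other tumours as ORR strata. Section 6.4.3 plans a by-patient listing for each cohort that includes cancer sub-type and best overall response. A listing is not a stratified estimate.

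**Step 5: size.** The number of Group 7 patients and their tumour mix are not available. The body of Expansion SAP section 4.3 and its Table 3 on the Group 7 design are withheld, as is the corresponding part of protocol section 12.3. The share of patients who would move to Cohort 6 therefore cannot be computed.

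**The case against.** The strongest defence is that section 6.1 can be read as a group-number rule throughout. The sentence introducing the cohorts refers to disease groups 1 through 8, every entry from Cohort 1 to Cohort 5 is tied to group numbers, and the Cohort 4 entry itself ends by naming group 7. The tumour-type rule also works badly on its own terms, since a breast or gastric patient in Group 8 would fall into two cohorts. On this reading the right patients are analysed and no numerator or denominator changes.

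Most of that stands, and it makes the group-number reading the better supported one. It does not close the matter. The same introductory sentence says the cohorts are based on disease type, and section 6.1 presents summary tables by disease type. A catch-all cohort that would otherwise be essentially empty suggests that some patients were expected to fall outside Cohorts 1–5. Even on the favourable reading, every by-cohort table would describe a multi-tumour basket as breast or gastric cancer.

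A second objection is that subgroup rules may exist in text that cannot be seen: Expansion SAP section 4.3 and Table 3, and protocol Figure 2 on Group 7 tumour types. This also stands. A reader might infer that the three subgroups have been dropped from the analysis. The documents support only the narrower statement that visible sections 6.1 and 6.4 do not name them as ORR strata. Whatever the withheld text says, it would not reconcile the Cohort 4 entry with sections 2 and 4.1 of the same SAP.

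**Conclusion.** The Cohort 4 definition is wrong as written and should be corrected. It is current SAP text, and both sides of the conflict are visible, so redaction does not explain it. The consequence depends on the reading. By group number, the by-cohort tables hold the right patients under a wrong label. By tumour type, the ORR for the FGFR2-amplification primary objective is estimated on a narrower tumour mix than the objective names.

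Two stronger readings should be resisted:

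- A reader might conclude that the basket ORR will in fact be computed on the wrong patients. The documents do not establish this, because it happens only under the less well supported reading.
- A reader might attach a loss of precision. With confidence-interval width roughly proportional to 1/√n, keeping two thirds of Group 7 multiplies the width by √(3/2) = 1.22, and keeping one third by √3 = 1.73. Those shares are assumptions with no basis in the documents, and the factor is 1 under the group reading. The size of the effect is unknown.

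Group 7 is also narrower than every FGFR2-amplified tumour. Tumour types belonging to earlier groups are excluded; FGFR2-amplified cholangiocarcinoma, for example, fits Group 4.

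**What to change.** In Expansion SAP section 6.1:

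- Define Cohort 4 as all treated patients assigned to disease group 7 (FGFR2 amplification, in a tumour type that no earlier group covers), and delete the breast/gastric wording.
- State that ORR for Cohort 4 is reported overall and for the ovarian, upper gastrointestinal and other-tumour subgroups, or refer to section 4.3 if the rule already stands there.
- Restrict Cohort 6 to treated patients not assigned to any of Groups 1–8, and say who is expected in it.

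One detail should be settled at the same time. Protocol Appendix H records that Amendment 7 changed the Group 7 requirement from FGF9 or FGF19 amplification to FGFR2 amplification. Whether anyone entered Group 7 under the previous requirement is not stated. If so, the SAP should say how they are shown, so that the group number and the FGFR2 description do not again select different patients.

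The cost is a few lines of SAP text and one subgroup table. Cancer sub-type is already planned for the by-patient listing, so no new data are needed.
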